11 SUPPORTING DOCUMENTATION AND OPERATIONAL CONSIDERATIONS

11.1 Regulatory, Ethical, and Study Oversight Considerations

11.1.1 Informed Consent Process

11.1.1.1 Consent/assent and Other Informational Documents Provided to participants

Consent forms describing in detail the study intervention, study procedures, and risks are given to the participant and written documentation of informed consent is required prior to starting intervention/administering study intervention. The following consent materials are submitted with this protocol:

- Informed Consent Form – Coordinating Center Template
- Informed Consent Form (Control Arm) – Coordinating Center Template

11.1.1.2 Consent Procedures and Documentation

No clinical investigator may involve a human being as a subject in research unless the investigator has obtained the legally effective informed consent from the subject, unless waived by the IRB. Informed consent is a process that is initiated prior to the individual's agreeing to participate in the study and continues throughout the individual's study participation. Consent forms will be Institutional Review Board (IRB)-approved and the participant will be asked to read and review the document. The investigator will explain the research study to the participant and answer any questions that may arise. A verbal explanation will be provided in terms suited to the participant's comprehension of the purposes, procedures, and potential risks of the study and of their rights as research participants. Participants will have the opportunity to carefully review the written consent form and ask questions prior to signing. The participants should have the opportunity to discuss the study with their family or surrogates or think about it prior to agreeing to participate. The participant will sign the informed consent document prior to any procedures being done specifically for the study. Participants must be informed that participation is voluntary and that they may withdraw from the study at any time, without prejudice. A copy of the informed consent document will be given to the participants for their records. The informed consent process will be conducted and documented in the source document (including the date), and the form signed, before the participant undergoes any study-specific procedures.

11.1.2 Study Discontinuation and Closure

This study may be temporarily suspended or prematurely terminated if there is sufficient reasonable cause. Written notification, documenting the reason for study suspension or termination, will be provided by the suspending or terminating party to study participants, investigator, funding sponsor, the and regulatory authorities. If the study is prematurely terminated or suspended, the Site Principal Investigator (PI) will promptly inform study participants and the Institutional Review Board (IRB) and will provide the reason(s) for the termination or suspension. Study participants will be contacted, as applicable, and be informed of changes to study visit schedule.

Circumstances that may warrant termination or suspension include, but are not limited to:

- Determination of unexpected, significant, or unacceptable risk to participants
- Demonstration of efficacy that would warrant stopping

Study may resume once concerns about safety, protocol compliance, and data quality are addressed, and satisfy the sponsor, IRB and/or Food and Drug Administration (FDA).

11.1.3 Confidentiality and Privacy

Participant confidentiality and privacy is strictly held in trust by the participating investigators, their staff, and the sponsor(s) and their interventions. This confidentiality is extended to cover testing of biological samples, MRI images, and genetic tests in addition to the clinical information relating to participants. Therefore, the study protocol, documentation, data, and all other information generated will be held in strict confidence. No information concerning the study or the data will be released to any unauthorized third party without prior written approval of the Coordinating Center.

All research activities should be conducted in as private a setting as possible.

The study monitor, other authorized representatives of the University of Florida, representatives of the Institutional Review Board (IRB), or regulatory agencies may inspect all documents and records required to be maintained by the investigator, including but not limited to, medical records (office, clinic, or hospital) for the participants in this study. The clinical study site will permit access to such records.

The study participant's contact information will be securely stored at each clinical site for internal use during the study. At the end of the study, all records will continue to be kept in a secure location for as long a period as dictated by the reviewing IRB and Institutional policies.

Study participant research data, which is for purposes of statistical analysis and scientific reporting, will be transmitted to and stored at the University of Florida. This will not include the participant's contact or identifying information. Rather, individual participants and their research data will be identified by a unique study identification number. The study data entry and study management systems used by clinical sites and by the University of Florida research staff will be secured and password protected. At the end of the study, all study databases will be de-identified and archived at the University of Florida.

11.1.4 Future Use of Stored Specimens and Data

11.1.4.1 MRI Data

MRI Data collected for this study will be analyzed and stored at Beth Israel Deaconess Medical Center. After the study is completed, the de-identified, archived data will be stored per local institution guidelines. Permission to transmit data to the Beth Israel Deaconess Medical Center will be included in the informed consent.

11.1.4.2 Tissue samples

With the participant's approval and as approved by local Institutional Review Boards (IRBs), de-identified biological samples will be shipped to the University of Florida for analysis. These samples could be used to research the causes of glioma, its complications and other conditions for which individuals with glioma are at increased risk, and to improve treatment. The researchers will also be provided with a code-link that will allow linking the biological specimens with the phenotypic data from each participant, maintaining the blinding of the identity of the participant during laboratory analyses.

During the conduct of the study, an individual participant can choose to withdraw consent to have biological specimens collected. However, withdrawal of consent to biosamples already collected will not be possible after analysis is underway.

When the study is completed, access to study data will be provided through the University of Florida. Residual samples will be returned or destroyed per standard practice.

11.1.6 Safety Oversight

Safety oversight will be under the direction of a Data and Safety Monitoring Board (DSMB) composed of individuals with the appropriate expertise, including oncology expertise. Members of the DSMB should be independent from the study conduct and free of conflict of interest, or measures should be in place to minimize perceived conflict of

interest. The DSMB will meet at least annually to assess safety and efficacy data on each arm of the study. The DSMB will operate under the rules of an approved charter that will be written and reviewed at the organizational meeting of the DSMB. At this time, each data element that the DSMB needs to assess will be clearly defined. The DSMB will provide its input to the Principal Investigator and IRB.

11.1.7 Clinical Monitoring

Clinical site monitoring is conducted to ensure that the rights and well-being of trial participants are protected, that the reported trial data are accurate, complete, and verifiable, and that the conduct of the trial is in compliance with the currently approved protocol/amendment(s), with Good Clinical Practice (GCP), and with applicable regulatory requirement(s).

- Monitoring and auditing for this study will be performed by the UF Coordinating Center.
- Details of ongoing site monitoring are documented in a Clinical Monitoring Plan (CMP).
 - A blend of centralized and on-site monitoring may be utilized based on site enrollment.
 - Monitoring will focus on targeted validation of primary outcome measures and any key safety measures determined throughout the study by DSMB. Validation will take place in the REDCap database, which will serve as the eCRF and source document repository for the study.
- Independent audits will be conducted by the UF Health Cancer Center at least annually.
 - Details of the auditing plan are documented in the UF Health Cancer Center manual.

11.1.8 Quality Assurance and Quality Control

Each clinical site will perform internal quality management of study conduct, data and biological specimen collection, documentation and completion. An individualized quality management plan should be on file to describe a site's ongoing quality management activities.

Quality control (QC) procedures will be implemented by the Coordinating Center beginning with the data entry system and data QC checks. Any missing data or data anomalies will be communicated to the site(s) for clarification/resolution; these data items should be addressed within 14 days of site notification.

Following written Standard Operating Procedures (SOPs), the monitors will verify that the clinical trial is conducted and data are generated and biological specimens are collected, documented (recorded), and reported in compliance with the protocol, Good Clinical Practice (GCP), and applicable regulatory requirements.

The investigational site will provide direct access to all trial related sites, source data/documents, and reports for the purpose of monitoring and auditing by the sponsor, and inspection by local and regulatory authorities.

11.1.9 Data Handling and Record Keeping

11.1.9.1 Data Collection and Management Responsibilities

Data collection is the responsibility of the clinical trial staff at the site under the supervision of the site investigator. The investigator is responsible for ensuring the accuracy, completeness, legibility, and timeliness of the data reported.

All source documents should be completed in a neat, legible manner to ensure accurate interpretation of data.

Hardcopies of the study visit worksheets will be provided for use as source document worksheets for recording data for each participant enrolled in the study. Data recorded in the electronic case report form (eCRF) derived

from source documents should be consistent with the data recorded on the source documents. It is permissible to use site worksheets or EMR records in place of visit worksheets if the same information is documented.

Clinical data (including adverse events (AEs), concomitant medications, and expected adverse reactions data) and clinical laboratory data will be entered into REDCap, a 21 CFR Part 11-compliant data capture system provided by the University of Florida Coordinating Center. The data system includes password protection and internal quality checks, such as automatic range checks, to identify data that appear inconsistent, incomplete, or inaccurate. Clinical data will be entered directly from the source documents.

Data should be entered into REDCap, including uploading related source documents, within 14 days of data collection.

For urgent data transmissions (Serious Adverse Events, etc.), fax and/or secure email transmission is acceptable with separate notification to the Coordinating Center confirming receipt of the records for review.

[contact]

Separate notification via email: *[contact]* or via [contact].

11.1.9.2 Study Records Retention

Study documents should be retained for at least 2 years have elapsed since the formal discontinuation of clinical development of the study intervention. These documents should be retained for a longer period, however, if required by local regulations. No records will be destroyed without the written consent of the sponsor, if applicable. It is the responsibility of the sponsor to inform the investigator when these documents no longer need to be retained.

Patients will be followed for survival status until death, loss to follow-up, withdrawal, or until study data collection is concluded. As stated earlier, it is anticipated that data collection will be complete in 5 years. At that time, the data set will then be cleaned and locked, and identifiable patient data will be coded for analysis.

11.1.10 Protocol Deviations

A protocol deviation is any noncompliance with the clinical trial protocol requirements. The noncompliance may be either on the part of the participant, the investigator, or the study site staff. As a result of deviations, corrective actions are to be developed by the site and implemented promptly.

These practices are consistent with GCP:

- Compliance with Protocol
- Quality Assurance and Quality Control
- Identification and correction of Noncompliance

It is the responsibility of the site investigator to use continuous vigilance to identify and report deviations within 14 days of identification of the protocol deviation, or within 14 days of the scheduled protocol-required activity. All deviations must be addressed in study source documents, and reported to Coordinating Center via the eCRF. Protocol deviations must be sent to the reviewing Institutional Review Board (IRB) per their policies. The site investigator is responsible for knowing and adhering to the reviewing IRB requirements.

11.1.1.11 Publication and Data Sharing Policy

The results of the clinical investigation will be made publicly available in case of positive or negative results following the completion of the trial.

11.1.1.12 Conflict of Interest Policy

The independence of this study from any actual or perceived influence, such as by the pharmaceutical industry, is critical. Therefore, any actual conflict of interest of persons who have a role in the design, conduct, analysis, publication, or any aspect of this trial will be disclosed and managed. Furthermore, persons who have a perceived conflict of interest will be required to have such conflicts managed in a way that is appropriate to their participation in the design and conduct of this trial. The study leadership in conjunction with the University of Florida has established policies and procedures for all study group members to disclose all conflicts of interest and will establish a mechanism for the management of all reported dualities of interest.

[name], the Study Chair and Sub-Investigator at the University of Florida, is a paid member of the medical advisory board of Novocure which provides funding for the study.

11.2 Additional Considerations

11.2.1 Guidance on Contraception

For the purposes of the proposed study, “highly effective” contraceptive methods are defined as those, alone or in combination, that result in a low failure rate (i.e., less than 1 percent per year) when used consistently and correctly, and include the following:

- Surgical sterilization at least 6 months before Study Drug administration
- Implants
- Levonorgestrel (LNG) and Copper T IUDs
- Sexual abstinence

Subjects who prefer methods which evidence a higher (6-9%) failure rate with typical use will be required to employ at least two methods of contraception concurrently. These methods include the following:

- Injectable hormone deposits
- Oral contraceptive pill
- Hormone patch
- Vaginal ring

Periodic abstinence (e.g., calendar, ovulation, symptothermal, post-ovulation methods) and withdrawal are NOT acceptable methods of contraception.

http://www.cdc.gov/reproductivehealth/unintendedpregnancy/pdf/contraceptive_methods_508.pdf for a list of contraceptive methods and effectiveness.

11.2.2 Enrollment Documentation Requirements

The following documentation is required for subject enrollment. All documents should be uploaded into the eCRF within 14 days of enrollment.

1. Signed and dated Informed Consent Form
2. Documentation of consent
3. Pathology Report including MGMT methylation status. If not feasible or indeterminate, must be stated. Indeterminate methylation status will be considered unmethylated.
4. Immunohistochemistry or next-generation sequencing Report (e.g. Foundation Medicine, TEMPUS, Caris, or similar CLIA-certified sequencing service)
5. Operative Report of biopsy or resection
6. Chemo/Radiation Radiology Report confirming total Gy delivered
 - a. An isodose map of the treatment area may be required (to adjudicate cases with suspected/possible new lesions outside the RT treatment field) before eligibility can be confirmed
7. Oncology Screening Visit Note
8. Screening MRI Report; RANO forms are not required at time of enrollment.
9. Screening labs with local lab reference ranges, reviewed and signed by local investigator
10. Relevant medical history
11. Concurrent medications
12. Steroid dose
13. Signed and dated enrollment checklist

11.2.2.1 Control Cohort Enrollment Documentation Requirements

The following documentation is required for control subject enrollment. All documents should be uploaded into the eCRF within 45 days of enrollment.

1. Signed and dated Informed Consent Form
2. Documentation of consent checklist
3. Pathology Report including MGMT methylation status. If not feasible or indeterminate, must be stated. Indeterminate methylation status will be considered unmethylated.
4. Immunohistochemistry or next-generation sequencing Report (e.g. Foundation Medicine, TEMPUS, Caris, or similar CLIA-certified sequencing service)
5. Screening MRI Report; RANO forms are not required at time of enrollment.
6. Signed and dated enrollment checklist

Additionally, the following data shall be entered into the eCRF at enrollment and source documentation included:

- a. KPS
- b. Resection Summary
- c. Chemo/Radiation Summary

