5.5.1 Screening

- Patients with newly diagnosed high-risk Grade II or III astrocytoma must undergo maximal safe resection (biopsy alone may be eligible).
- Patients must undergo chemoradiotherapy: concomitant 75mg/m² daily temozolomide with 80% prescribed dose completed and RT with minimal RT dose of 40 Gy delivered.
- Within three weeks prior to beginning adjuvant temozolomide, all patients will undergo a Baseline contrast-enhanced MRI of the brain.
- Within two weeks prior to beginning adjuvant temozolomide, all patients will undergo the following assessments:
 - Medical History and demographics
 - Medication History
 - Steroid Dose (recorded)
 - MGMT methylation status (if feasible, required for stratification)
 - Tumor Tissue sample – verify availability of FFPE, pathology slides, and/or frozen sample(s)
 - RANO assessment
 - Complete physical examination
 - Neurological status and KPS
 - CBC with differential
 - Pregnancy test (urine or serum) – WOCBP only
 - Biochemistry panel (Electrolytes, creatinine, bilirubin, liver enzymes)
 - Quality of life questionnaires (EORTC QLQ-C30/BN20, and MMSE)

No study-specific procedures may be performed prior to obtaining informed consent. However, assessments performed according to standard of care, prior to consent, may be used to fulfill the screening requirement if they are part of the patient’s medical record within the specified timeframe.

See Section “Enrollment Documentation Requirements” for a complete list of patient enrollment documentation.

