10 STATISTICAL CONSIDERATIONS

10.1 Statistical Hypotheses

- Primary Efficacy Endpoint: overall survival (OS)

Control arm: the control arm will consist of both historical and contemporaneous control patients. Historical controls will consist of TERT mutation-only astrocytoma patients treated and followed by the participating sites between January 1, 2016 and May 20, 2019. As described above, these patients will have received standard treatment and would have met first tier inclusion/exclusion criteria for the study. Data for these patients will be collected via chart review. Contemporaneous controls will also consist of patients who qualify for the trial and receive standard treatment but decide not to proceed with the Optune experimental treatment because of personal preference. This personal preference must be non-medical in nature. Based on clinical experience, most commonly this non-medical patient personal preference preventing Optune use will be unwillingness to shave his/her head and/or unwillingness to wear a visible medical device on his/her head most of the day.

- N = 90 patients total in an expected mixture ranging between 80 historical controls and 10 contemporaneous controls to 60 historical controls and 30 contemporaneous controls.
- Assumed median survival = 22 months (based on Figure 3A in Eckel-Passow et al [12])
- Follow-up = up to 60 months for the historical controls, up to 60 months for the contemporaneous controls

Experimental treatment arm: TERT mutation-only astrocytoma patients who will receive standard treatment plus TFields therapy at one of 15 participating centers.

- N = 90 patients

- Assumed accrual rate = 2.5 patients/month accumulated over 15 centers
- Accrual period = 36 months
- Follow-up period after the end of accrual = 24 months
- Assumed survival time distribution = Weibull with accelerating hazard and proportional hazards

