10.2 Sample Size Determination

To assess sample size requirements for detecting an improvement in median overall survival (OS) in the experimental treatment arm relative to the historical control arm, we initially assumed 60 to 90 patients receiving standard treatment and follow-up between 1-2016 and 5-2019 would be available for chart review. We assumed that these historical control patients would have a maximum follow-up time of 60 months. For the experimental treatment, we assumed an accrual rate of 2.5 patients per month across 15 participating centers and an accrual period of 36 months, yielding an enrollment of 90 patients in the experimental arm. The patients in the experimental arm would be followed for an additional 24 months after the end of accrual. We considered improvements in median survival ranging from 4 to 8 months to be of clinical interest. We also assumed that survival times would follow a Weibull distribution with proportional hazards and an accelerating hazard function (shape parameter $k=2.0$, estimated from Figure 3A in Eckel-Passow et al [12]. We also considered a more slowly accelerating Weibull shape parameter of $k=1.8$. Under these assumptions, the power to detect **improvements** in median OS using a one-sided log-rank test (one-sided $\alpha=0.05$) are summarized in Table 10 for selected combinations of historical control sample size, Weibull shape parameter, and number of months improvement in median OS [detectable effect size methodology adapted from (Wu and Xiong, 2014)]. We then explored the effect of mixing historical and contemporaneous controls in select mixtures into a single control arm, noting a very slight improvement in power to detect improvements in survival. Overall, a control arm sample size of 90 patients, in historical/contemporaneous control mixtures of 90+0, 80+10, 70+20, and 60+30 all have at least 80% power to detect improvements in survival between 6 and 8 months.

TABLE 10: POWER TO DETECT M MONTHS IMPROVEMENT IN MEDIAN OVERALL SURVIVAL UNDER SELECTED SCENARIOS

Accrual rate (N/mo)	Accrual period (mos)	Follow-up period (mos)	Trial N	Hx Ctl+ Contemp N	Weibull shape k	Power to detect M months improvement in median OS at one-sided $\alpha=0.05$ using the log-rank test				
						M = 4	5	6	7	8
2.5	36	24	90	50+ 0	2.0	0.525	0.667	0.782	0.866	0.922
2.5	36	24	90	60+ 0	2.0	0.565	0.711	0.823	0.899	0.946
2.5	36	24	90	70+ 0	2.0	0.598	0.745	0.853	0.922	0.962
2.5	36	24	90	80+ 0	2.0	0.626	0.773	0.876	0.938	0.972

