10.2.1 Analysis of Primary and Secondary Endpoints and Correlative Studies

We will compare OS and progression-free survival (PFS) between historical control and experimental treatment arms using the log-rank test (we will also collect PFS data via chart review for the historical control patients). For our correlative studies, we will use the independent-sample t test to compare mean mutation burden between patient samples treated with RT+temozolomide or RT+temozolomide+TTFields. We may perform the same comparison within a linear regression framework if the need arises to adjust for any potential confounders for the effect of TTFields in our correlative studies.

To investigate the influence of electric field and energy deposition in the tumor on outcomes, we will use the Wilcoxon rank sum test to compare the electric field and specific absorption ratio parameters between: responders and non-responders; subjects with progression-free survival \geq and $<$ 1 year; subjects with overall survival \geq and $<$ 2 years; and subjects with overall survival \geq and $<$ 1.5 years. We will estimate Pearson correlation coefficients to assess the correlation of OS and PFS with electric field or specific absorption ratio parameters.

We may stratify the patients by MGMT methylation status, extent of resection, or a combination of the two.

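### Coding indeterminate MGMT as unmethylated would bias an MGMT-stratified comparison of device and control patients if indeterminate rates differ between the cohorts; the powered unstratified log-rank test is unaffected

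*Combined protocol and SAP*

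**What the plan says.** Item 3 of the enrolment documents for device patients (Section 11.2.2) and for controls (Section 11.2.2.1) asks for a pathology report with MGMT status. Both add "If not feasible or indeterminate, must be stated" and then "Indeterminate methylation status will be considered unmethylated". No category is assigned to a result that was not feasible.

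The documents differ on how MGMT will be used. Section 5.5.1 lists "MGMT methylation status (if feasible, required for stratification" among the screening items. Section 10.2.1 says only "We may stratify the patients by MGMT methylation status, extent of resection, or a combination of the two".

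The specified comparison is in Section 10.2.1: "We will compare OS and progression-free survival (PFS) between historical control and experimental treatment arms using the log-rank test". Section 10.2 sizes the trial "using a one-sided log-rank test" at alpha 0.05, and Table 10 mentions no strata. There is no rationale for the coding rule and no sensitivity analysis of it.

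**The concern.** The comparison is not randomised. Section 10.1 expects 60 to 80 of the 90 controls to be historical, and Sections 9 and 9.5 take control data from charts, the historical ones from patients finishing chemoradiation between January 2016 and May 2019. Device patients have MGMT recorded at screening. Nothing in the design makes the proportion of indeterminate results equal in the two cohorts.

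Some indeterminate tumours are methylated. Coding them all as unmethylated puts them in the wrong stratum. If the proportions differ, that stratum has a different methylated share in each cohort, and a stratified OS or PFS comparison carries the imbalance as an apparent treatment effect. More indeterminates among controls would mask a benefit; more among device patients would create one. A stratification meant to reduce confounding would then add bias.

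**Working it through.** **Inputs from the documents.** "Assumed median survival = 22 months" for controls (Section 10.1); 90 patients per arm; Weibull survival with proportional hazards and shape k = 2.0, also 1.8; one-sided alpha 0.05; 36 months of accrual plus 24 months of follow-up, so 24 to 60 months for device patients and up to 60 for controls. On the effect, Section 10.2 says "We considered improvements in median survival ranging from 4 to 8 months to be of clinical interest".

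**Inputs not in the documents (assumed).** Methylated share 40% (30-50% for the range); methylated versus unmethylated hazard ratio 0.5 or 0.7; indeterminate rates of 5% to 30%; indeterminacy unrelated to true methylation within each cohort.

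**Step 1: reproduce Table 10.** HR = (22/(22+M))^k, so for M = 6 and k = 2.0, HR = (22/28)² = 0.617. Power = Φ(|ln HR| × √[1/(1/d_c + 1/d_e)] − 1.645), where d_c and d_e are expected deaths. With every control followed for 60 months, d_c = 89.5 and d_e = 67.6: 0.482 × √38.5 − 1.645 = 1.35, a power of 0.911. With control follow-up spread over 24 to 60 months the same formula gives 0.896, against 0.894 in the table. For k = 1.8 it gives 0.826 against 0.820. The planned unstratified test is reproduced, and MGMT coding does not enter it.

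**Step 2: the mechanism by hand.** With methylated share p and indeterminate rate q, the methylated fraction of the coded unmethylated stratum is pq/(pq + 1 − p). For p = 0.4:

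- q = 5%: 0.02/0.62 = 3.2%
- q = 20%: 0.08/0.68 = 11.8%
- q = 30%: 0.12/0.72 = 16.7%

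With an MGMT hazard ratio of 0.5, the starting hazard in that stratum, relative to a pure unmethylated group, is 1 − 0.5 × fraction: 0.984, 0.941 and 0.917. With no device effect, the apparent device-to-control hazard ratio in that stratum is therefore:

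- controls 20%, device 5%: 0.984/0.941 = 1.05
- controls 30%, device 5%: 0.984/0.917 = 1.07
- controls 5%, device 20%: 0.941/0.984 = 0.96
- controls 5%, device 30%: 0.917/0.984 = 0.93

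Simulated stratified hazard ratios under no effect (k = 2.0) agree. Across methylated shares of 30-50% and MGMT hazard ratios of 0.5 and 0.7 they are 1.02-1.06 at 20% v 5%, 1.03-1.09 at 30% v 5%, and 0.91-0.97 at 5% v 30%. Equal rates (10/10% or 20/20%) give 0.99-1.01.

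**Step 3: error rates, 90 v 90, 40% methylated.** Simulated stratified log-rank tests. Controls are followed for 60 months in the 5/30 rows, and both arms for 24-60 months in the 5/20 rows and in the 20/5 and 30/5 power rows.

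| Indeterminate, controls/device | MGMT HR | k | Measure | Coded unmethylated | Separate stratum |
|---|---|---|---|---|---|
| 5/20% | 0.5 | 1.8 | type I error | 0.080 | about 0.05 |
| 5/20% | 0.7 | 1.8 | type I error | 0.059 | about 0.05 |
| 5/20% | 0.7 | 2.0 | type I error | 0.068 | about 0.05 |
| 5/30% | 0.5 | 2.0 | type I error | 0.111 | about 0.05 |
| 5/30% | 0.7 | 2.0 | type I error | 0.078 | about 0.05 |
| 20/5% | 0.5 | 1.8 | power, 6 months | 0.72 | 0.79 |
| 20/5% | 0.7 | 2.0 | power, 6 months | 0.865 | 0.875 |
| 30/5% | 0.5 | 1.8 | power, 6 months | 0.66 | 0.76 |
| 30/5% | 0.5 | 2.0 | power, 6 months | 0.75 | 0.84 |
| 20/20% | 0.5 | 1.8 | power, 6 months | 0.784 | 0.780 |

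A separate run at 5/30% with MGMT hazard ratio 0.5 gave 0.12 in place of 0.111. The simulation standard error is about √(0.11 × 0.89/3000) = 0.006, so the two are compatible. The unstratified log-rank test kept type I error at 0.048-0.054 in every scenario examined.

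**The case against.** The strongest reply is that the affected analysis is optional. Section 10.2.1 specifies a log-rank test without strata, Table 10 powers that test, and the MGMT rule leaves it alone. This stands. A reader might infer that the planned primary OS test is biased; the documents do not support that.

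A second reply is that the rule is the same in both cohorts, that MGMT comes from the pathology report in both, that controls are treated at the same institutions, and that Section 5.5.1 accepts standard-of-care results obtained before consent. A reader might infer from the chart-review design that indeterminate rates do differ, or that the rule favours the device. No passage gives a rate for either cohort, so unequal rates are a plausible risk and the direction is open. False positives arise only if device patients have more indeterminate results.

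Third, MGMT is not the only prognostic variable available. Section 10.2.1 names extent of resection alongside it, and Section 9.5 also collects KPS and demographics for controls.

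Fourth, indeterminate status must already be stated, so the information is kept and can be analysed differently later. This also stands, and it makes the remedy cheap.

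What survives is narrower. MGMT is one of two stratifiers the plan names, Section 5.5.1 calls it required for stratification, and the only coding given for an indeterminate result is one that is neutral only when the rates match.

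**Conclusion.** The point holds for any MGMT-stratified OS or PFS comparison and for nothing else. With unequal indeterminate rates the rule biases that comparison; with equal rates it does not.

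Across the assumed values the effect runs from negligible to moderate. Type I error is about 0.06 to 0.11 when device patients have the higher rate (20-30% v 5%). The power loss for a 6-month gain is about 1 to 10 points when controls do. Not all of a shortfall below 80% is due to the rule: at k = 1.8, MGMT hazard ratio 0.5 and 30% v 5%, the separate stratum itself reaches only 0.76.

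These sizes rest on assumed prevalence, MGMT effect and indeterminate rates, and would change with them. Severity is minor to moderate, and higher only if the stratified test becomes the primary analysis. The disagreement between Sections 5.5.1 and 10.2.1 over whether stratification is required, and the missing category for results that were not feasible, follow from the text alone and need no assumption.

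**What to change.** 1. In Sections 11.2.2 and 11.2.2.1, replace the recoding sentence with three analysis categories: methylated, unmethylated, and indeterminate or not feasible. The status already has to be stated, so no new data are needed.
2. In Section 10.2.1, make the third category its own stratum in any MGMT-stratified analysis of OS or PFS.
3. Report the frequency of that category by cohort.
4. Keep the indeterminate-as-unmethylated coding as a sensitivity analysis only.
5. Reconcile Section 10.2.1 with Section 5.5.1, and state before analysis whether the OS test is stratified by MGMT.

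The cost is an eCRF code, a few sentences, and a slight loss of information. At equal 20% rates, power was 0.784 with the present coding and 0.780 with a separate stratum. At 30% v 5% the third stratum would hold about 27 controls (0.30 × 90) and 4 or 5 device patients (0.05 × 90 = 4.5), so it would contribute little to the test. The correction is complete only if indeterminacy is unrelated to true methylation within each cohort, and the plan should say so.
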